4.3.2 Specific Adverse Events

The incidence rates (%) and event counts of TEAEs by system organ class (SOC) and by preferred term (PT) will be summarized by treatment group. The table will be organized

so that adverse event categories (SOC) are reported in upper case letters and specific adverse events (PT) are reported in lowercase.

The incidence rates (%) and event counts of TEAEs by system organ class (SOC) and by preferred term (PT) will be summarized by treatment group restricted to events with at least 5% incidence in either group.

Tables will summarize the incidence rates (%) of specific TEAE PTs, sorted by descending incidence of PT in the active drug group.

The incidence rates (%) and event counts of drug related TEAEs by SOC and by PT will be summarized by treatment group.

The incidence rates (%) and event counts of serious drug related TEAEs by SOC and by PT will be summarized by treatment group.

Tables will summarize the incidence rates (%) of serious TEAE PTs, sorted by descending incidence of PT in the active drug group.

The incidence rates (%) and event counts of serious drug related TEAEs by SOC and by PT will be summarized by treatment group.

4.3.3 Severity of Adverse Events

The incidence rates (%) and event counts of severe TEAEs by SOC and by PT will be summarized by treatment group.

Tables will summarize the incidence rates (%) of severe TEAE PTs, sorted by descending incidence of PT in the active drug group.

Counts of drug related TEAEs in the active drug group will be summarized by severity, SOC and PT will be provided. Similarly, counts of drug related TEAEs in the placebo group will be summarized by severity, SOC and PT.

4.3.4 Comparisons Between Subjects with and without a TEAE

Tables will provide a comparison of demographic and baseline disease characteristics between patients in the active treatment group experiencing and not experiencing at least one Treatment Emergent Adverse Event.

4.3.5 Safety Listings

A comprehensive set of safety listings will be provided for all subjects in the Safety Analysis Set. Adverse event listings will include SOC, PT, relationship, severity, onset and resolution dates (and study days), and action taken.

4.3.6 Clinical Laboratory Values

Clinical Laboratory data at each timepoint and change from baseline will be summarized using descriptive statistics and shift tables (based on normative ranges). (See Protocol NI03-CV19-001 Section 12.3 Laboratory Assessments and PPD Lab Manual for normative ranges.)

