Serious decreased platelets have been reported from post-marketing surveillance. Symptoms included subcutaneous hemorrhage, oral hemorrhage, and epistaxis. The number of days until the onset was within 1 month after administration in most cases. Possible idiopathic thrombocytopenic purpura was suspected in some reported cases. In subacute and chronic toxicity studies of the drug, the decrease in platelets was not observed, and the mechanism of pathogenesis remains unknown.

Hepatic Function Disorder, Jaundice

Hepatic function disorder and jaundice (both with unknown frequency), accompanied by extreme elevation of aspartate aminotransferase (AST), alanine aminotransferase (ALT), and gamma-glutamyl transferase (GGT), and alkaline phosphatase (ALP) have been reported from post-marketing surveillance. Initial symptoms included general fatigue, nausea and vomiting, and jaundice. Most of disorders occurred without subjective symptoms and identified by medical examinations. The duration from the beginning of dosage to onset was 12 months in many cases. Some disorders occurred (identified) after the end of administration of the drug. In subacute and chronic toxicity studies of the drug, hepatic function abnormal was not observed, and the mechanism of pathogenesis remains unknown.

Hyperkalemia

Serious hyperkalemia has been reported from post-marketing surveillance, although the frequency is unknown due to spontaneous reporting. Most of the disorders occurred without subjective symptoms and were identified by medical examinations. Abnormal electrocardiograms or electrocardiogram abnormalities with clinical symptoms (general fatigue and sensation of heaviness in chest) were observed in some cases. The duration from the beginning of dosage to the onset was within 2 months in most cases. In subacute and chronic toxicity studies of the drug, abnormal changes in potassium levels were not observed, and the mechanism of pathogenesis remains unknown.

Overall, the evidence of clinical activity and the AE profile observed support a positive benefit-to-risk ratio for subjects with COVID-19 who are treated with camostat mesilate.

Details regarding known or anticipated benefits and risks, as well as reasonably anticipated AEs for camostat mesilate may be found in the IB ([Sagent Pharmaceuticals, 2020](#)).

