10.1 Study Visits

10.1.1 Screening/Baseline and Day 1 Visit

The following procedures and assessments will be done at the onsite Screening/Baseline and Day 1 visit:

- Verify subject has written notification from a local laboratory confirming COVID-19 infection within 72 hours of randomization (i.e., Day 1). In most instances, the Screening/Baseline visit will occur on the same date as Day 1. If needed, the Screening/Baseline may occur before Day 1 as long as randomization can be completed within the 72-hour window.
- Obtain informed consent
- Review of inclusion/exclusion criteria, including urine pregnancy test, if applicable
- Assign a subject ID number (ID number = XXX site number followed by 001, 002, 003 subject number)
- Obtain mid-turbinate nasal swab sample to be sent to the central laboratory to test for a baseline assessment and to test for viral shedding of COVID-19 by RT-PCR
- Draw blood for central laboratory testing
- Record demographics, medical history (including current COVID-19 symptoms), and concomitant medications
- Obtain vital signs (height, weight, heart rate, blood pressure, SpO2)
- Measure oral body temperature
- Perform randomization and dispensing of study drug
- Provide subject with instructions for accessing eDiary portal for collection of daily information
- Administer first dose of study drug after all assessments are completed
- Record of any TEAEs

10.1.2 Onsite Visits on Day 7, Day 15, Unscheduled Visit, Early Termination Visits / Telephone Visits on Day 21, Day 28

The following procedures and assessments will be done on Day 7, Day 15, Day 21, Day 28, and early termination by telephone or at onsite visits:

- Verify subject compliance for completing daily eDiary entries by accessing the web portal for the subject's eDiary
- Review concomitant medications and record any TEAEs
- Assess vital signs (heart rate, blood pressure, SpO2) during on-site visits only
- Measure oral body temperature
- Draw blood for central laboratory testing (Day 15, Unscheduled Visit and Early Termination) during on-site visits only

- Obtain mid-turbinate nasal swab sample for viral shedding test (Day 7, Day 15, and Early Termination Visits) for central laboratory during on-site visits only

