10.3 Study Procedures

Assessments and their timing are to be performed as outlined in the Schedule of Assessments (Table 1). Section 12.3 specifies laboratory assessment samples to be obtained.

Assessments and procedures scheduled at a visit where study drug is administered should be performed before administration of study drug unless otherwise indicated in the Schedule of Assessments (Table 1).

Efficacy assessments are described in Section 11 and include recording of hospitalization or death for any cause (if not hospitalized), resolution of fever, overall survival rate, and viral shedding.

Safety assessments are described in Section 12 and include concomitant medications, vital signs, laboratory assessments, pregnancy test, and AEs.

The investigator may, at his/her discretion, arrange for a subject to have an unscheduled assessment, especially in the case of AEs that require follow-up or are considered by the investigator to be possibly related to the use of study drug. The unscheduled visit page on the eCRF must be completed.

Study discontinuation procedures are described in Section 8.5.

Follow-up of AEs and SAEs leading to study discontinuation is discussed in Section 8.5.

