Table 14.2.2.1 – Counts and Percentages Surviving to Days 15 and 28 Days by Treatment Group in ITT	Table 14.2.2.1	ITT
Table 14.2.2.2 – Counts and Percentages Surviving to Days 15 and 28 Days by Treatment Group in PP1	Table 14.2.2.2	PP1
Table 14.2.2.3 – Counts and Percentages Surviving to Days 15 and 28 Days by Treatment Group in PP2	Table 14.2.2.3	PP2
Table 14.2.3.1 – Time to Resolution of Fever by Treatment in ITT Analysis Set	Table 14.2.3.1	ITT
Table 14.2.3.2 – Time to Resolution of Fever by Treatment in PP1 Analysis Set	Table 14.2.3.2	PP1
Table 14.2.3.3 – Time to Resolution of Fever by Treatment in PP2 Analysis Set	Table 14.2.3.3	PP2
Figure 14.2.4.1 – Kaplan-Meier Time to Resolution of Fever in ITT	Figure 14.2.4.1	ITT
Figure 14.2.4.2 – Kaplan-Meier Time to Resolution of Fever in PP1	Figure 14.2.4.2	PP1
Figure 14.2.4.3 – Kaplan-Meier Time to Resolution of Fever in PP2	Figure 14.2.4.3	PP2
Table 14.2.5.1 – Time to COVID-19 Hospitalization/ER visit or Death by Treatment in ITT	Table 14.2.5.1	ITT
Table 14.2.5.2 – Time to COVID-19 Hospitalization/ER visit or Death by Treatment in PP1	Table 14.2.5.2	PP1

TLF Name	TLF Number	Population
Table 14.2.5.3 – Time to COVID-19 Hospitalization/ER visit or Death by Treatment in PP2	Table 14.2.5.3	PP2
Figure 14.2.6.1 – Kaplan-Meier Time to COVID-19 Hospitalization/ER visit by Treatment in ITT	Figure 14.2.6.1	ITT
Figure 14.2.6.2 – Kaplan-Meier Time to COVID-19 Hospitalization/ER visit by Treatment in PP1	Figure 14.2.6.2	PP1
Figure 14.2.6.3 – Kaplan-Meier Time to COVID-19 Hospitalization/ER visit by Treatment in PP2	Figure 14.2.6.3	PP2
Table 14.2.7.1 – Proportion of Subjects with No Viral Shedding at Days 7, 15, and at Early Termination in ITT	Table 14.2.7.1	ITT
Table 14.2.7.2 – Proportion of Subjects with No Viral Shedding at Days 7, 15, and at Early Termination in PP1	Table 14.2.7.2	PP1
Table 14.2.7.3 – Proportion of Subjects with No Viral Shedding at Days 7, 15, and at Early Termination in PP2	Table 14.2.7.3	PP2
Table 14.2.8.1 – Shift Table of Fever Severity Categories	Table 14.2.8.1	ITT
Table 14.2.8.2 – Shift Table of Fever Severity Categories	Table 14.2.8.2	PP1
Table 14.2.8.3 – Shift Table of Fever Severity Categories	Table 14.2.8.3	PP2
Tables Safety		
Table 14.3.1.1 - Overall Summary of Adverse Events by Treatment	Table 14.3.1.1	SP
Table 14.3.1.2 – Adverse Events Occurring in 5% of Subjects in Either Treatment Group by MedDRA System Organ Class and Preferred Term	Table 14.3.1.2	SP

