Subject ID	Treatment	Adverse Event Description	Onset Date/ Resolution Date	Study Day of Onset/ Duration	Severity	Relationship to Study Treatment	Outcome	Action Taken with Study Treatment	MedDRA® System Organ Class	MedDRA® Preferred Term
xxxxxx	Camostat mesilate	xxxxxxxx	YYYY-MM-DD YYYY-MM-DD	YY/ YY	XXXXX	XXXXXX	XXXXXX	XXXXXXX	XXXXXXX	XXXXXXX
		xxxxxxxx	YYYY-MM-DD YYYY-MM-DD	YY/ YY	XXXXX	XXXXXX	XXXXXX	XXXXXXX	XXXXXXX	XXXXXXX
xxxxxx	Placebo	xxxxxxxx	YYYY-MM-DD YYYY-MM-DD	YY/ YY	XXXXX	XXXXXX	XXXXXX	XXXXXXX	XXXXXXX	XXXXXXX
		xxxxxxxx	YYYY-MM-DD YYYY-MM-DD	YY/ YY	XXXXX	XXXXXX	XXXXXX	XXXXXXX	XXXXXXX	XXXXXXX

Program: xxxxx.sas Database Lock Date: DDMMYYYYY: Run Date: DDMMYYYYY

Table 14.3.2.2: Listing of Serious Adverse Events

Programming Notes: Use the same layout as Table 14.3.2.1 – Select only Serious Adverse Events

Table 14.3.2.3: Listing of Grade 3 or Grade 4 or Grade 5 Adverse Events

Programming Notes: Use the same layout as Table 14.3.2.1 – Select only Grade 3 or Grade 4 or Grade 5 Adverse Events

Table 14.3.2.4: Listing of Adverse Events Leading to Study Drug Discontinuation

Programming Notes: Use the same layout as Table 14.3.2.1 – Select only Adverse Events leading to study drug discontinuation

DRAFT Table 14.3.4.1
Summary of Alanine Aminotransferase (ALT) (U/L) by Study Day and Treatment
Intent-to-Treat Population

Study Day	Statistic	Camostat mesilate (N=xxx)		Placebo (N=xxx)	
		Observed	Change	Observed	Change
Baseline (Day 1) ^a	n	xxx	xxx	xxx	xxx
	Mean	xxx.x	xxx.x	xxx.x	xxx.x
	Std Deviation	xxx.x.	xxx.x.	xxx.x.	xxx.x.
	Median	xxx.x	xxx.x	xxx.x	xxx.x
	Min, Max	xxx, xxx	xxx, xxx	xxx, xxx	xxx, xxx
Day 7	n	xxx	xxx	xxx	xxx
	Mean	xxx.x	xxx.x	xxx.x	xxx.x
	Std Deviation	xxx.x.	xxx.x.	xxx.x.	xxx.x.
	Median	xxx.x	xxx.x	xxx.x	xxx.x
	Min, Max	xxx, xxx	xxx, xxx	xxx, xxx	xxx, xxx
Day 15	n	xxx	xxx	xxx	xxx
	Mean	xxx.x	xxx.x	xxx.x	xxx.x
	Std Deviation	xxx.x.	xxx.x.	xxx.x.	xxx.x.
	Median	xxx.x	xxx.x	xxx.x	xxx.x
	Min, Max	xxx, xxx	xxx, xxx	xxx, xxx	xxx, xxx
Notes: N=Number of subjects in the Intent-to-Treat Population; n=Number of subjects with an assessment at the specified time point. Change=Change from Baseline; ^a Baseline is the last value prior to treatment for a subject. It is used in the change from baseline. Program: xxxxx.sas Database Lock Date: DDMMYYYYY: Run Date: DDMMYYYYY					

Table 14.3.4.1.2: Summary of Alanine Aminotransferase (ALT) (U/L) by Study Day and Treatment – Safety Population

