Programming Notes: Use the same layout as Table 14.3.4.1.2 – change population to the safety population

**DRAFT Table 14.3.4.1.3
Shift of Alanine Aminotransferase (ALT) (U/L) by Study Day and Treatment**

		Camostat mesilate (N=xxx)								Placebo (N=xxx)							
		Low		Normal		High		Missing		Low		Normal		High		Missing	
Study Day		n	%	n	%	n	%	n	%	n	%	n	%	n	%	n	%
Baseline	---	xx	xx.x	xx	xx.x	xx	xx.x	xx	xx.x	xx	xx.x	xx	xx.x	xx	xx.x	xx	xx.x
Day 15	Low	xx	xx.x	xx	xx.x	xx	xx.x	xx	xx.x	xx	xx.x	xx	xx.x	xx	xx.x	xx	xx.x
	Normal	xx	xx.x	xx	xx.x	xx	xx.x	xx	xx.x	xx	xx.x	xx	xx.x	xx	xx.x	xx	xx.x
	High	xx	xx.x	xx	xx.x	xx	xx.x	xx	xx.x	xx	xx.x	xx	xx.x	xx	xx.x	xx	xx.x
	Missing	xx	xx.x	xx	xx.x	xx	xx.x	xx	xx.x	xx	xx.x	xx	xx.x	xx	xx.x	xx	xx.x
Notes: N=Number of subjects in the Intent-to Treat Population; n=Number of subjects with an assessment at the specified time point. ^a Baseline is the last value prior to treatment for a subject. Program: xxxxx.sas Database Lock Date: DDMMMYYYY: Run Date: DDMMMYYYY																	

Table 14.3.4.1.4: Shift of Alanine Aminotransferase (ALT) (U/L) by Study Day and Treatment – Safety Population

Programming Notes: Use the same layout as Table 14.3.4.1.3 – change population to the safety population

DRAFT Figure 14.3.4.1.5
Boxplots of Laboratory Parameters by Study Day and Treatment: Alanine Aminotransferase (ALT) (U/L)
Intent-to-Treat Population

[figure not shown]

Figure 14.3.4.1.6: Boxplots of Laboratory Parameters by Study Day and Treatment: Alanine Aminotransferase (ALT) (U/L) – Safety Population

Programming Notes: Use the same layout as Table 14.3.4.1.5 – change population to the safety population

Table 14.3.4.2.1 - Summary of Aspartate Aminotransferase (AST) (U/L) by Study Day and Treatment – ITT Population

Programming Notes: Use the same layout as Table 14.3.4.1.1 – Change ALT to AST

Table 14.3.4.2.2 - Summary of Aspartate Aminotransferase (AST) (U/L) by Study Day and Treatment – Safety Population

Programming Notes: Use the same layout as Table 14.3.4.1.1 – change ALT to AST and population to the safety population

Table 14.3.4.2.3 – Shift of Aspartate Aminotransferase (AST) (U/L) by Study Day and Treatment – ITT Population

Programming Notes: Use the same layout as Table 14.3.4.1.3 – Change ALT to AST

Table 14.3.4.2.4 - Shift of Aspartate Aminotransferase (AST) (U/L) by Study Day and Treatment – Safety Population

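### The draft laboratory tables have no place for the Early Termination and unscheduled blood results that the protocol collects; a baseline-to-worst shift table would use them

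*SAP*

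**What the plan says.** - **SAP 4.3.6** gives the rule: "Clinical Laboratory data at each timepoint and change from baseline will be summarized using descriptive statistics and shift tables". It names no visits and does not say where Early Termination or unscheduled samples go.
- **Protocol 10.1.2** lists the post-baseline draws: "Draw blood for central laboratory testing (Day 15, Unscheduled Visit and Early Termination) during on-site visits only". Table 1 of the protocol agrees and has no laboratory mark at Day 7.
- **SAP appendix, summary shell**, "Summary of Alanine Aminotransferase (ALT) (U/L) by Study Day and Treatment": rows for Baseline (Day 1), Day 7 and Day 15.
- **SAP appendix, shift shell**, "Shift of Alanine Aminotransferase (ALT) (U/L) by Study Day and Treatment": rows for Baseline and Day 15, with categories Low, Normal, High and Missing.
- **Other analytes.** The AST, ALP and GGT shift shells copy this layout through the note "Use the same layout as Table 14.3.4.1.3 – Change ALT to AST". Potassium and platelets appear only in the list of tables, under matching titles by study day.
- **Contrast.** The viral-shedding table does name the early visit: "Proportion of Subjects with No Viral Shedding at Days 7, 15, and at Early Termination in ITT". No laboratory table title does so.

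**The concern.** Change from baseline in laboratory parameters is a declared safety endpoint, and SAP 2.3.3 singles out platelets, liver tests and potassium. Protocol 10.3 says that an unscheduled assessment may be arranged, "especially in the case of AEs that require follow-up or are considered by the investigator to be possibly related to the use of study drug". Early Termination blood may be the only post-baseline result from a subject who leaves during treatment. The tables therefore omit samples that are likely to be informative about safety, although the same central laboratory measured them.

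Protocol 5.3 says of the reported hepatic disorders: "Most of disorders occurred without subjective symptoms and identified by medical examinations". It says much the same of hyperkalemia. For harms of this kind, an objective comparison of measured values between arms is the purpose of a laboratory table.

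**Working it through.** No stated figure bears on this point, so the check sets the sampling schedule against the tables.

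**Step 1. Which samples have a row?**

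| Post-baseline occasion | Blood scheduled or allowed (Protocol Table 1, 10.1.2) | Summary shell row | Shift shell row |
|---|---|---|---|
| Day 7 | No | Yes | No |
| Day 15 | Yes | Yes | Yes |
| Unscheduled | Yes, at the investigator's discretion | No | No |
| Early Termination | Yes | No | No |

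Of the three occasions on which blood can be drawn, the shells display one. The summary shell also carries one row for which no draw is scheduled.

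**Step 2. Could an Early Termination sample be read as the Day 15 sample?** The SAP has no analysis window. Protocol 8.5 places the visit 3 to 7 days after the last dose, and Table 1 allows 1 day either side. For a last dose on Day 5, the visit falls on Day 5 + 3 = 8 to Day 5 + 7 = 12, and at the latest on Day 12 + 1 = 13. The Day 15 visit with its own tolerance starts at Day 15 − 1 = 14. Such a sample is outside even the visit tolerance. After a later last dose it may fall inside, but no rule says that it then counts as Day 15.

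**Step 3. What happens to each kind of subject?**
- Leaves the study early, has an Early Termination sample, has no Day 15 sample: counted as Missing in the shift table, whatever the value.
- Has an abnormal unscheduled sample and a Day 15 sample: appears at the Day 15 value. If that has returned to normal, the subject is shown as Normal. The subject is not Missing, but the abnormal value is not shown.
- Stops the drug but is followed on and sampled at Day 15: shown correctly.

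**Step 4. How many subjects?** The documents do not say. The nearest figure is the allowance for loss to follow-up in SAP 4.1.4: 200 − 186 = 14 on camostat and 100 − 93 = 7 on placebo. This does not estimate the affected group. It does not separate subjects with an Early Termination sample from those with none, and it is not a forecast of treatment discontinuation.

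**Step 5. Is any analyte left out altogether?** Protocol Table 2 collects total and direct bilirubin, and Protocol 5.3 describes jaundice among the significant reactions. In the SAP list, bilirubin appears only in the baseline laboratory table (14.1.3). The post-baseline tables cover ALT, AST, ALP, GGT, potassium and platelets.

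**The case against.** The strongest reply is that these subjects are captured elsewhere. The protocol synopsis has clinically significant laboratory changes recorded as adverse events. SAP 4.3 tabulates events causing discontinuation, serious events and grade 3 to 5 events, and SAP 4.3.5 promises comprehensive safety listings. Protocol 13 says that all data will be listed. A subject who stops because of liver, platelet or potassium toxicity should therefore appear in the adverse event output. **This stands**, and it confines the point to the laboratory tables. It does not dispose of it. The adverse event route depends on a judgement of clinical significance, a listing is not a comparison between arms, and the SAP's list of tables contains no laboratory listing.

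Second, with no draw scheduled between baseline and Day 15, a silent abnormality would seldom prompt early stopping and would usually be found at Day 15. **This stands** as a limit on how often toxicity itself causes the missing value. It does not help a subject who leaves for another reason and has an abnormal Early Termination result.

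Third, stopping the drug need not cost the Day 15 sample, because Protocol 8.5 intends follow-up to Day 28, and an unscheduled sample does not replace Day 15. **Both stand**, and step 3 allows for them.

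Fourth, the shells are marked draft, SAP 4.3.6 does not in terms exclude Early Termination, the boxplot figures are not shown, and the potassium and platelet layouts are inferred from titles. **All true.** The draft status makes correction easy, but the text of 4.3.6 supplies no rule that would lead a programmer to a different table.

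**Conclusion.** The point holds for the laboratory tables as drafted. Central-laboratory results from Early Termination and unscheduled visits have no defined place in them, and subjects who leave before Day 15 can be Missing despite a measured value. What is lost is the objective count by arm of abnormal values, including those that no investigator judged clinically significant.

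Two stronger readings are tempting, and the documents support neither.
- A reader might infer that the known harms of the drug are under-counted in the trial's safety reporting as a whole. The adverse event tables and listings also receive clinically significant changes and discontinuations, so this is not shown.
- A reader might infer that the tables make camostat look safer than it is. That requires early leaving with abnormal values to be commoner on camostat than on placebo, and no figure supports this. The Missing category is shown by arm, so an imbalance in missing values would be visible, although the values themselves would not.

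The size cannot be derived. The rates in Protocol 5.3, such as 12 hepatic function abnormalities in 4224 subjects (0.3%), are reported adverse events in other indications, not rates of out-of-range values in this population. The conclusion assumes only that the shells are programmed as drafted and that the unprinted potassium and platelet shells follow the ALT layout. It is a cheap and worthwhile improvement to a descriptive analysis and does not affect the efficacy conclusions.

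**What to change.** 1. In SAP 4.3.6 and shells 14.3.4.x.3 and 14.3.4.x.4, add a baseline-to-worst post-baseline shift in the Safety Population for ALT, AST, ALP, GGT, bilirubin, potassium and platelets. Bilirubin needs a new shell.
2. Define worst as the most abnormal central-laboratory value at any post-baseline visit, including unscheduled and Early Termination visits. State the direction for each analyte. Reserve Missing for subjects with no post-baseline sample at all.
3. Print the number of post-baseline samples per arm beside the table.
4. Keep the Day 15 shift table alongside.
5. Reconcile the Day 7 row of the summary shell with the sampling schedule.

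The cost is SAP and shell wording and one derived record per subject and parameter, with no new samples. The downside is that subjects with extra samples have more chances to show an abnormal value. The sample counts by arm let the reader judge this, and the Day 15 table gives a view with one fixed sampling time.

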5.3 Clinical Risks/Benefits of Camostat Mesilate

Camostat mesilate has been available in Japan for 30 years where it is used for the treatment for relief of the acute symptoms of chronic pancreatitis and postoperative reflux esophagitis. The following is taken directly from the package insert for Foipan[®] (camostat mesilate) and is considered an important precaution:

Foipan Tablet[®] 100 mg should not be administered to patients with severe chronic pancreatitis requiring dietary restrictions such as gastric aspiration, or abstaining from food or drink.

In terms of the AEs seen in humans with chronic pancreatitis, in 3806 subjects subject to reporting of adverse reactions in the clinical trial at the approval stage and in the post-marketing surveillance study, 83 adverse reactions (including abnormal clinical laboratory test values) were observed in 69 of 3806 subjects (1.8%). The main adverse reactions were 15 cases of rash (0.4%), 9 cases of itching (pruritus; 0.2%), 10 cases of nausea (0.3%), 7 cases of abdominal discomfort (0.2%), and 6 cases of abdominal bloating (0.2%).

From a postoperative reflux esophagitis investigation for FOIPAN performed up to the time of approval and in the Drug Use Investigation, 75 AEs were reported in 57 (1.3%) out of 4224 subjects. The major AEs were 12 (0.3%) cases of hepatic function abnormalities such as increased AST and ALT, 8 (0.2%) cases of diarrhea, and 5 (0.1%) cases of nausea.

The Foipan[®] package insert also details the following significant adverse reactions:

Symptoms of Shock and Anaphylaxis

Shock or anaphylactoid symptoms were reported from post-marketing surveillance. No specific antibody production has been reported with the drug in antigenicity studies in animals. However, in view of time course of symptom development (symptoms developed within 30 minutes after dosing in most cases), initial symptoms (dermatitis such as welts, itching sensation, and erythema, vertigo, feeling poorly, dull headache, sweaty, cold sweat, edema/swelling, dyspnea, and decrease in blood pressure), and subjects who had a past history of administration of this drug had experienced symptoms of hypersensitivity (e.g., urticaria, itching sensation and edema), these may have occurred due to anaphylactic reactions.

Thrombocytopenia

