13.4 Safety Analysis

All reported AEs will be coded using the latest version of the Medical Dictionary for Regulatory Activities (MedDRA). The incidence of TEAEs will be included in incidence tables. Events with missing onset dates will be included as treatment-emergent. If a subject experiences more than 1 occurrence of the same AE, the occurrence with the greatest severity and the closest association with the study drug will be used in the summary tables. SAEs, grade 3 or 4 TEAEs, and TEAEs causing discontinuation will be summarized using discrete summaries by system organ class and preferred term for each treatment group. All AEs will be listed by subject, along with information regarding onset, duration, relationship and severity to study drug, action taken with study drug, treatment of event, and outcome. TEAEs will be summarized by severity and relationship separately.

Clinical laboratory data and vital signs will be summarized using descriptive statistics, including mean values and mean change from baseline values, as well as numbers of subjects with values outside limits of the normal range at each time point.

Summary tables will be provided for concomitant medications initiated during the study period.

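### The SAP plans no by-arm count of subjects passing a severity threshold for liver tests, potassium or platelets, and its draft table list names no post-baseline bilirubin output

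*SAP*

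**What the plan says.** **Known harms.** Protocol 5.3, citing the Japanese package insert, describes hepatic disorder and jaundice "accompanied by extreme elevation of aspartate aminotransferase (AST), alanine aminotransferase (ALT), and gamma-glutamyl transferase (GGT") and alkaline phosphatase. It also states: "Serious hyperkalemia has been reported from post-marketing surveillance" and "Serious decreased platelets have been reported from post-marketing surveillance". Of the hepatic cases it says: "Most of disorders occurred without subjective symptoms and identified by medical examinations". It says much the same of hyperkalemia.

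**Endpoint.** SAP 2.3.3 lists change from baseline in laboratory parameters as a safety endpoint and names platelets, liver tests and potassium.

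**Analysis.** Protocol 13.4 plans means and mean changes, "as well as numbers of subjects with values outside limits of the normal range at each time point". SAP 4.3.6 plans descriptive statistics and "shift tables (based on normative ranges". The ALT summary shell gives n, mean, SD, median, minimum and maximum, for observed value and change, by arm, at Baseline, Day 7 and Day 15. The ALT shift shell has the classes Low, Normal, High and Missing, at Baseline and Day 15. Boxplots by day and arm are listed.

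**Parameters.** Protocol Table 2 includes total and direct bilirubin. The SAP table list names post-baseline outputs for ALT, AST, ALP, GGT, potassium and platelets. Bilirubin is named only in baseline Table 14.1.3.

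**Sampling.** Protocol Table 1 and Section 10.1.2 schedule post-baseline blood draws at Day 15, at unscheduled visits and at early termination.

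**The concern.** The harms of interest are defined by how far a value moves, but the only categorical analysis asks whether it left the normal range. A move from just below to just above the upper limit counts the same as a move to ten times the limit. A subject who is High at baseline and rises tenfold does not change class. Minimum and maximum give the single worst value per arm and visit, not the number of subjects with such values, and they cannot show whether transaminases and bilirubin rose in the same subject.

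Two gaps add to this. Jaundice is part of the labelled reaction, but its laboratory marker has no named post-baseline output. And a subject who stops early with a severe value contributes an early-termination sample for which the drafted shells have no row; at Day 15 that subject may appear only as Missing.

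At stake is how clearly the safety objective can be answered. Protocol 7.2 gives 200 mg QID (800 mg/day) against an approved 200 mg TID in Japan, so readers will look for these signals by arm.

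**Working it through.** **1. Figures in the plan.** The point rests on no stated figure, but two are relevant. Protocol 5.3 gives "12 (0.3%) cases of hepatic function abnormalities such as increased AST and ALT" among 4224 subjects: 12/4224 = 0.28%, which reproduces the rounded figure. The arm sizes come from Protocol 13.1: exact enumeration of the two-sided Fisher test for 30% versus 15% with 92 and 183 subjects gives 80.2% power against the stated 80%. With the drop-out allowance, the arms are 200 and 100.

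**2. How many cases to expect.** At 0.28%, the expected number in 200 camostat subjects is 200 × 0.00284 = 0.57, and P(at least one) = 1 − (1 − 0.00284)^200 = 43%. That rate is for any hepatic abnormality. The documents give no rate for severe changes. At assumed rates of 0.5%, 1% and 2%, P(at least one) is 63%, 87% and 98%. A handful of cases at most is the realistic setting.

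**3. What the shift table shows (illustration on assumed inputs).** Suppose a share *b* of each arm has a mild High value, and 3 further camostat subjects have a severe one. The documents give no value for *b*.

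| *b* | High, camostat | High, placebo | Fisher p |
|---|---|---|---|
| 5% | 13/200 = 6.5% | 5/100 = 5% | 0.80 |
| 20% | 43/200 = 21.5% | 20/100 = 20% | 0.88 |
| 40% | 83/200 = 41.5% | 40/100 = 40% | 0.90 |

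If the three were already among the High subjects, the row would not change at all.

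**4. What the mean shows.** Three subjects at *m* times the upper limit instead of 1 times raise the arm mean by 3(*m* − 1)/200 upper limits: 0.06 for *m* = 5, 0.135 for *m* = 10 and 0.285 for *m* = 20.

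**5. What a threshold count shows.** It would read 3/200 (1.5%) versus 0/100, Fisher p = 0.55. Four versus 0 gives p = 0.31, and 8 versus 0 gives p = 0.056. The count makes cases visible; it does not supply a test.

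**6. Sampling against shells.** Day 15 is the only routine post-baseline draw. The summary shell nevertheless has a Day 7 row, for which no routine blood draw is scheduled. Neither ALT shell has a row for the worst value, unscheduled samples or early termination.

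**7. The adverse event route.** Clinically significant laboratory changes become AEs on the investigator's judgement (Protocol synopsis, safety assessments). Protocol Table 3 grades severity by effect on everyday activities, so a change without symptoms need not be rated severe. SAP 4.3 tabulates CTCAE grade 3 to 5 events, but the protocol does not define those grades, and the shell of Table 14.3.1.1 simply pairs Severe with Grade 3.

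**The case against.** A reader might infer that laboratory data are analysed only as means and shifts, or that severe cases would appear in no between-arm table. The documents do not support either reading.

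- **Spread and extremes are shown by arm.** Assume 4 of 200 camostat subjects rise by 200 U/L in ALT, with a change SD of 20 U/L. The mean moves by 0.02 × 200 = 4 U/L, but the camostat SD becomes √(20² + 0.02 × 0.98 × 200²) = 34 U/L against 20 U/L. In a simulation of 20,000 such trials, the camostat maximum change always exceeded twice the placebo maximum. The boxplots would show the same. A subject already High who rises further is also caught by the change columns.
- **The adverse event route is real.** Protocol 12.3 requires the investigator to review and sign every laboratory report and to follow up clinically significant values. The resulting AEs enter by-arm tables, and SAP 4.3.5 and Protocol 13 promise listings.
- **Bilirubin is not excluded.** SAP 4.3.6 does not limit its parameters and points to Protocol 12.3, which includes bilirubin. The output list is marked draft, and it is not exhaustive: SAP 4.3.7 covers oxygen saturation, which also has no listed post-baseline output.
- **Context.** Protocol 5.3 puts hepatic onset at 12 months in many cases, against 14 days of dosing here. Protocol 5.2.2 describes an ongoing blinded trial that includes 300 mg TID for 28 days, in which none of the six reported serious events was a hepatic, potassium or platelet event.

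All of this stands, and it limits the point to a partial gap. It does not supply the missing count. The maximum is one subject per arm and visit, listings are not counts by arm, and the AE tables rest on judgement and on an activity-based scale. The hepatic onset argument carries less weight elsewhere: Protocol 5.3 puts platelet onset mostly within 1 month and hyperkalemia mostly within 2 months.

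**Conclusion.** The point holds in a limited form. Neither document plans a by-arm count of subjects passing a severe level for liver tests, potassium or platelets. No post-baseline bilirubin output is named. The drafted shells have no row for unscheduled or early-termination values. Severe cases would not vanish, because minimum and maximum, SD, boxplots, AE tables and listings remain, but a reader could not tell from the laboratory tables how many subjects per arm had one.

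The numerical illustrations rest on assumed severe-event rates, background rates and SD. They show the mechanism and do not forecast this trial. It would also be wrong to infer that a threshold count would detect a difference: at 3 or 4 cases against none it does not. The primary analysis is unaffected. This is a low-cost improvement to a named safety endpoint, and it should be made while the shells are still in draft.

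**What to change.** In SAP 4.3.6, for the Safety population:

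- Add by-arm counts, or a baseline-to-worst shift, of each subject's worst post-baseline value, including unscheduled and early-termination samples. Classify by CTCAE grade or, for the liver tests, by multiple of the upper limit. Cover ALT, AST, ALP, GGT, total bilirubin, potassium and platelets.
- Add total bilirubin to the post-baseline summary and shift tables.
- Add one display of peak ALT/AST against peak total bilirubin by arm. For most subjects the peak will be the single Day 15 value, so label the display accordingly.
- State that these outputs are descriptive.
- Reconcile the Day 7 row of the ALT summary shell with the blood-draw schedule in Protocol Table 1.

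The cost is SAP and shell wording and a few more tables. All values are already collected at the central laboratory, and trial procedures do not change.
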